#### Fractures (including vertebral fractures)

Fractures will be coded according to MedDRA and will be classified by PT and SOC. Fracture listings will be presented by participant, SOC and PT.

The incidence of all reported fractures will be tabulated separately. In addition, summary tables will be presented by maximum intensity and drug relationship (investigator-reported causality assessment).

**PAGE 65 OF 287** 

#### Pregnancy

Confirmation of an absence of pregnancy will be included in the participant data listings using the Safety Exposed Population only.

Incidence of all pregnancies will be summarised for those exposed and unexposed to palovarotene in the Safety Exposed Population. For these analyses, the pregnancy will be considered as exposed to palovarotene if it occurs whilst the participant is using the medicinal product or within 2 days after stopping the product (based on the estimated date of conception).

For participants who become pregnant while enrolled in FOPal, whether exposed or not to palovarotene, pregnancy characteristics and outcomes, pregnancy-related AEs through the first year postpartum, and birth and developmental outcomes through the infant(s)' first year of life will be descriptively summarised by palovarotene exposure status (exposed and unexposed).

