# 9.2.1 Palovarotene-exposed Cohort

#### 9.2.1.1 Inclusion Criteria

To be included in the palovarotene-exposed cohort, the participants should fulfil all the following inclusion criteria:

- (1) Paediatric (8 years to less than 18 years of age for girls and 10 years to less than 18 years of age for boys) and adult participants with FOP who have been prescribed palovarotene (prior to and independently of the decision to enrol the patient in the FOPal registry study) by their treating physician, as per local label;
- (2) Signed informed consent as per local regulations must be obtained and maintained. Consent/assent from the participant should be obtained as appropriate before any registry study data collection is conducted. If applicable, parents or legally authorised representatives must give signed informed consent.

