# Pregnancy Testing for Exposed Participants

Participants will be assessed for child-bearing status and pregnancy prevention measures prior to receiving palovarotene. As per local label, pregnancy testing will be carried out with a confirmation of absence of pregnancy for as long as the participant receives palovarotene and for one month after stopping. These conditions also apply to participants who are not currently sexually active unless the prescriber considers that there are compelling reasons to indicate that there is no risk of pregnancy.

Pregnancy is contraindicated during treatment with palovarotene, therefore if a participant is pregnant or has a positive pregnancy test at any time during the registry study, this will result in immediate discontinuation of palovarotene. A pregnant participant will be followed throughout her pregnancy and through the first year postpartum to monitor pregnancy-related AEs and the birth and developmental outcomes of the infant(s)' through the first year of life (see Section 11.1.3.1).

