# 9.7 Data Analysis

# 9.7.1 Analyses Population Definitions

For the purposes of analyses, the following populations are defined:

- Enrolled Population including all participants who signed the ICF.
- Safety Exposed Population including all enrolled participants who have taken at least one dose of marketed palovarotene at any time before the signed ICF or during the study; A distinction will be made depending on time of start of marketed palovarotene:
  - Palovarotene prevalent users: participants who received palovarotene before or at the time of ICF signed;
  - Palovarotene incident users: participants who started receiving palovarotene after enrolment in the registry. Two time periods will be defined: Period 1 is from enrolment to last day before the first dose of marketed palovarotene; Period 2 is after the first dose of marketed palovarotene.
- Safety Exposed Paediatric Population including all paediatric participants (8 years to less than 18 years of age for girls and 10 years to less than 18 years of age for boys) from the Safety Exposed Population.
- Safety Unexposed Population including all enrolled participants who never received at least one dose of marketed palovarotene before or during their participation in the registry;
- Safety Unexposed Paediatric Population including all paediatric participants (8 years to less than 18 years of age for girls and 10 years to less than 18 years of age for boys) from the Safety Unexposed Population.

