# 9.7.2 Sample Size Determination

The FOPal registry study aims to enrol a minimum of 67 participants with FOP treated with palovarotene and 33 participants with FOP not treated with palovarotene. Approximately half of the participants in each cohort (exposed and unexposed) will be paediatric (8 years to less than 18 years of age for girls and 10 years to less than 18 years of age for boys).

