#### 9.7.3.1 Statistical Analyses – General Considerations

The statistical analyses will be performed by an external SP, managed by the sponsor's Medical Affairs Biometry Department.

Statistical evaluation will be performed using Statistical Analysis System (SAS)® (Version 9.2 or higher).

No formal statistical testing will be performed and all the analyses will be primarily descriptive in nature. When appropriate and unless otherwise specified, 2-sided 95% CI will be displayed and if p-values are presented, they will be for exploratory purposes only.

Descriptive summary statistics will include the number of documented data, number of missing data and the following:

- Mean, standard deviation, 95% CI of the mean/median when appropriate, median, minimum and maximum for continuous variables;
- Frequency count and percentages for categorical nominal variables.

Missing data will not be replaced but will be summarised in all relevant tables.

Percentages will be based on the number of non-missing observations.

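### Pregnancy incidence is assigned to the whole Safety Exposed Population, which includes males and girls who cannot become pregnant; used as the denominator, that set dilutes the incidence

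*Protocol*

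**What the plan says.** The Pregnancy paragraph of Protocol Section 9.7.3.4 sets the analysis: "Incidence of all pregnancies will be summarised for those exposed and unexposed to palovarotene in the Safety Exposed Population". Within that population a pregnancy counts as exposed if conception falls during use of the drug or within 2 days of stopping it.

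Section 9.7.1 gives the definition: "Safety Exposed Population including all enrolled participants who have taken at least one dose of marketed palovarotene at any time before the signed ICF". Participants whose first marketed dose comes after consent also belong to it. Section 9.7.1 defines five populations, and none is limited to females or to participants of child-bearing potential. Section 9.2.1.1 admits "Paediatric (8 years to less than 18 years of age for girls and 10 years to less than 18 years of age for boys) and" adults of either sex. Section 9.7.2 adds that "The FOPal registry study aims to enrol a minimum of 67 participants with FOP treated with palovarotene" and that "Approximately half of the participants in each cohort (exposed and unexposed) will be paediatric". No expected sex mix is given for the registry.

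The data needed to identify who is at risk are planned. Section 9.3.2.7 says: "Participants will be assessed for child-bearing status and pregnancy prevention measures prior to receiving palovarotene". Section 9.2.7.3 also captures changes in fertility status at follow-up for exposed participants.

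On denominators, Section 9.7.3.1 gives only the general rule: "Percentages will be based on the number of non-missing observations". The protocol does not say whether pregnancy incidence is per participant or per unit of time.

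**The concern.** An incidence should be computed among people who can have the event. The set named here contains males and pre-pubertal girls, who add to the denominator and can never add to the numerator. Section 9.7.3.4 shows that the authors do restrict elsewhere: its growth outcomes are analysed in growing children only.

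Incidence of pregnancy is a named secondary endpoint (Section 9.3.1.2). Section 11.1.3.1 calls the drug highly teratogenic, and Section 7.3.1 records no pregnancies in the development programme. Readers will therefore look to this registry for the first incidence figure, and a diluted one would be falsely reassuring.

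There is a second difficulty. The paragraph splits pregnancies by exposure at conception, and one participant can spend time both on and off the drug. A single head count of participants cannot serve as the denominator for both strata. Follow-up also varies widely: the study runs up to 11 years, with a minimum of 1 year of data per participant (Section 9.2.4).

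**Working it through.** The protocol states no pregnancy incidence, so there is no figure of its own to reproduce. The check asks how far a whole-set denominator dilutes the result.

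**Inputs**
- Exposed cohort: N = 67, the minimum in Section 9.7.2, with half paediatric.
- Female share f: not given for the registry. The nearest figure is the treated group aged at least 8 (girls) or 10 (boys) years in the completed phase III study (Section 7.3.2, N = 79): 36/79 = 45.6% female and 43/79 = 54.4% male, which matches the printed percentages. Section 7.1 reports no sex predisposition, so 50% is also plausible. 55% is added to show the direction.
- Share g of paediatric girls who are of child-bearing potential: not given, so varied from 0 to 1.
- All adult women are counted as at risk. This is conservative, because it lowers the dilution.

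**Formula**

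Share at risk: s = f × (0.5 + 0.5g). Dilution factor if all N are in the denominator: 1/s.

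Example at f = 45.6%, g = 0.5: s = 0.456 × 0.75 = 0.342; at risk 67 × 0.342 = 22.9; factor 1/0.342 = 2.92.

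| Female share f | g = 1 (all females at risk) | g = 0.5 | g = 0 (adult women only) |
|---|---|---|---|
| 45.6% | 30.6 at risk, 2.19 | 22.9, 2.92 | 15.3, 4.39 |
| 50% | 33.5, 2.00 | 25.1, 2.67 | 16.8, 4.00 |
| 55% | 36.9, 1.82 | 27.6, 2.42 | 18.4, 3.64 |

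**What one pregnancy would look like at f = 45.6%**
- Whole set: 1/67 = 1.5%
- All females: 1/30.6 = 3.3%
- At risk with g = 0.5: 1/22.9 = 4.4%
- Adult women only: 1/15.3 = 6.5%

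**When the factor falls below 2**

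This happens when more than half of the set is at risk, that is 34 or more of 67. Treating the number at risk as binomial with probability s, the chance is 23% at f = 45.6%, g = 1; 0.4% at f = 45.6%, g = 0.5; 50% at f = 50%, g = 1; and 1.8% at f = 50%, g = 0.5.

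**The case against.** The strongest reply is that the protocol names an analysis set and not a denominator. Section 9.7.3 leaves technical detail to a separate SAP, and under the non-missing rule males with no pregnancy record might drop out. This stands in part: dilution follows only if the whole set is used. But the rule does not say how not-applicable participants are handled, and a male with no pregnancy recorded could as easily be counted as a non-event. The protocol did choose a population here, and a SAP that follows it literally would carry the problem forward.

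Second, Section 9.7.4 plans subgroup analyses by age group and gender. If applied to this endpoint, the female row would remove the sex part of the dilution. It would not separate girls who are of child-bearing potential from those who are not, and no sex-by-age table is promised.

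Third, every pregnancy is reported and followed individually, and few are expected. This is correct. Counts, characteristics and outcomes do not depend on the denominator, and with zero events the point estimate stays at zero.

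A reader might go further and infer that incidence is certain to be understated at least twofold. The documents do not support that. The denominator is not stated separately, and the 45.6% female share is borrowed from another study. With every female counted as at risk, the factor is exactly 2.0 at 50% female and lower above that. Nor does the protocol present pregnancy incidence as a measure of how well prevention works; its objective is only descriptive.

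**Conclusion.** The point holds in conditional form. The population fixed for pregnancy incidence includes participants who cannot become pregnant, and no at-risk set is defined. If that population is the denominator, incidence is diluted about 2.2-fold against all females at a 45.6% female share, 2.0-fold at 50% and 1.8-fold at 55%. The dilution reaches about 4-fold if few girls are of child-bearing potential. These figures rest on 67 exposed participants, half of them paediatric, the same female share in children and adults, and all adult women at risk. The sex mix and the maturity of the girls are assumptions, because the protocol gives neither for the registry.

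**What to change.** In Section 9.7.3.4, restrict pregnancy incidence to members of the Safety Exposed Population while they are of child-bearing potential, using the child-bearing and fertility status already collected. Report pregnancies per person-years at risk, with the number of pregnancies beside the rate.

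- **Exposed time:** time on palovarotene and up to 2 days after stopping, to match the definition already in that paragraph.
- **Unexposed time:** all other time in the registry, including Period 1 of incident users (enrolment to the day before first dose, Section 9.7.1) and time after the 2-day window. Counting only from first dose would drop Period 1.
- **Start of time at risk:** no earlier than attainment of child-bearing potential, so that a girl enters the denominator when she becomes at risk.

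Period 1 is best shown on its own line. Section 9.2.8 withdraws an unexposed participant who becomes pregnant, so those who go on to a first dose will rarely have had a pregnancy in that period.

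The cost is protocol and SAP wording, somewhat more derivation work, and a reported incidence that will look less favourable. No new assessment is needed in exposed participants. For those who move over from the unexposed cohort, whose schedule (Table 4) lists no pregnancy testing, child-bearing status before the first dose may have to be derived from age, sex and Tanner stage.

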# 8.2.2 Secondary Objectives

For participants with FOP exposed and unexposed to palovarotene:

- To describe the range of motion (ROM) as assessed by the Cumulative Analogue Joint Involvement Scale (CAJIS) for FOP;
- To describe the use of assistive devices and adaptations for daily living;
- To describe the physical function using age-appropriate forms of the Fibrodysplasia Ossificans Progressiva-Physical Function Questionnaire (FOP-PFQ);
- To describe the parameters of lung function (observed and % predicted forced vital capacity (FVC), observed and % predicted forced expiratory volume in one second (FEV1), absolute and % predicted FEV1/FVC ratio, observed and % predicted diffusion capacity of the lung for carbon monoxide (DLCO)) at Baseline and over time;
- To describe the physical and mental health (participants ≥15 years old) and overall quality of life (QoL) (participants <15 years old) using age-appropriate forms of the Patient-Reported Outcomes Measurement Information System (PROMIS) Global Health Scale;
- To describe the flare-up frequency;
- To describe any movement mobility change by body location and annually;
- To describe the number of locations impacted by movement mobility change per participant annually;
- To describe the movement mobility outcomes (change in extra bone growth and change in movement), causes and associated symptoms if preceded by a flare-up event by body location;
- To describe the frequency, severity, outcome and descriptive details of any fractures (including bone fracture and vertebral fractures).
- To describe the incidence of pregnancy.

For participants with FOP exposed to palovarotene who become pregnant while enrolled in FOPal:

- To describe pregnancy characteristics and outcomes;
- To describe pregnancy-related AEs through the first year postpartum;
- To describe birth and developmental outcomes through the infant(s)' first year of life.

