**PAGE 40 OF 287** 

- a Follow-up Visits are recommended every 6 months, or as per local label.
- b If participant <18 years (or the legal age of consent in the jurisdiction in which the study is taking place), assent and parent or legally authorised representative consent will also be required.
- c This includes a general assessment, dermatologic, lymph nodes, HEENT, chest, cardiac, abdomen, limb/extremities, musculoskeletal, neurologic and other.
- d Not expected in the context of a telephone/video visit.
- e Collected for growing children. Assessment as per local label.
- f Linear height within 6 to 12 months prior to and at the Baseline Visit.
- g Vital signs to be collected are respiratory rate, blood pressure and heart rate.
- h Participants will be assessed for child-bearing status and pregnancy prevention measures. As per local label, pregnancy testing is carried out with a confirmation of absence of pregnancy monthly if the participant receives palovarotene and one month after stopping. These conditions also concern participants who are not currently sexually active unless the prescriber considers that there are compelling reasons to indicate that there is no risk of pregnancy.
- i This includes a period of two months prior to the signed informed consent date.
- i Not applicable for pregnant participants.
- k Spirometry obtains the lung function parameters of observed and % predicted FVC and FEV1 and the absolute and % predicted FEV1/FVC ratio. The DLCO test obtains observed and % predicted DLCO which provides information on the efficiency of gas transfer from alveolar air into the bloodstream.
- 1 This includes number of flare-ups over the past 12 months before the signed informed consent date.
- m Spinal health assessment to be performed using radiological imaging (e.g. CT, X-ray, scintigraphy, etc).
- n AE, SAE, Special Situation and AESI collection begins once the informed consent has been signed.
- o Paper-based patient-reported questionnaires.

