# 9.2.8 Registry Study Discontinuation/Withdrawal

The participant can withdraw (or be withdrawn if the subject is a child upon legal representative's decision) from the FOPal registry study at any time. The date and primary reason for withdrawal should be recorded in the eCRF as well as whether the participant stopped or not palovarotene for exposed participants.

Should the participant withdraw from the study, no further data will be collected, nevertheless, data collected up to the time of the withdrawal will be kept for analysis, safety and integrity of study results.

The participant will be withdrawn from the FOPal registry study if:

- The participant enrols in any interventional clinical trial for FOP, or,
- For exposed participants: the participant is no longer receiving palovarotene (except if palovarotene is discontinued due to a safety concern or pregnancy, in such cases the participant will be monitored for safety, see Section 11.4 for follow-up of AEs and Section 11.1.3.1 for follow-up of pregnancies).
- For unexposed participants: the participant becomes pregnant or starts a treatment for FOP other than palovarotene. In case the participant starts palovarotene, they should have the option to remain in the registry. Previously unexposed participants starting palovarotene and remaining in the registry will follow the exposed naïve participants schedule (Table 2) from the first marketed palovarotene intake.

Investigators, participants or/and parents may decide to stop the participation in the FOPal registry study at any time without consequences on the normal participant clinical care.

PAGE 50 OF 287

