# 9.3.1.2 Secondary Endpoints

For participants with FOP exposed and unexposed to palovarotene:

- Raw values and change from Baseline in CAJIS total score at each Follow-up Visit;
- Raw values and shift from Baseline in use of assistive devices and adaptations for daily living at each Follow-up Visit;
- Raw values and change from Baseline in % of worst score for total score, upper extremities subscore and mobility subscore using age-appropriate forms of the FOP-PFQ at each Follow-up Visit;
- Raw values and change from Baseline in observed and % predicted FVC at each Follow-up Visit;
- Raw values and change from Baseline in observed and % predicted FEV1 at each Follow-up Visit;
- Raw values and change from Baseline in absolute and % predicted FEV1/FVC ratio at each Follow-up Visit;

PAGE 51 OF 287

- Raw values and change from Baseline in observed and % predicted DLCO at each Follow-up Visit;
- Raw values and change from Baseline in physical and mental function (mean global physical and mental health score converted into T-scores) for participants ≥15 years old and overall QoL (mean total score converted into T-scores) for participants <15 years old using age-appropriate forms of PROMIS Global Health Scale at each Follow-up Visit;
- Annualised frequency of flare-ups, categorised by overall occurrence;
- Number of locations impacted by movement mobility change per participant annually and change from Baseline;
- Any movement mobility change (better movement/the same movement/slightly worse movement/moderately worse movement/severely worse movement) by body location and annually;
- Evolution of locations impacted by movement mobility change (how many times a location is impacted) per body location, annually and change from baseline;
- Movement mobility outcomes (change in extra bone growth and change in movement), causes, associated symptoms if preceded by a flare-up event by body location;
- Frequency, severity, outcome and descriptive characteristics of any fractures, overall and at each Follow-up Visit, categorised by location;
- Annualised frequency and descriptive characteristics of bone fractures, categorised by overall occurrence and location;
- Incidence of pregnancy.

For participants with FOP exposed to palovarotene who become pregnant while enrolled in FOPal:

- Pregnancy characteristics and outcomes;
- Pregnancy-related AEs through the first year postpartum;

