**PAGE 77 OF 287** 

- Infant outcomes (from one month to one year, end of follow-up period):
  - Infant death;
  - Postnatal growth deficiency;
  - Infant developmental delay;
  - Infant hospitalisation due to serious illness.

Details of all pregnancies in participants will be collected from the signing of the ICF and the participant will be followed through the first year postpartum to monitor pregnancy-related AEs, and the birth and developmental outcomes through the infant(s)' first year of life. The following monitoring schedule is recommended for data collection:

- Baseline;
- Mid-pregnancy;
- Estimated Due Date (EDD);
- EDD + 6 months;
- EDD + 12 months.

For live-born infants, data should be assessed at 3 timepoints during the data collection: at EDD; EDD + 6 months; and EDD + 12 months.

Information regarding any pregnancies must be collected on the electronic data collection tool or the "Adverse Event and Other Safety Events Report Form for Company-Sponsored Non-Interventional Studies" (134232-FOR) if the electronic data collection tool is unavailable. Pregnancy information, including birth and developmental status of the infant will also be collected in the Drug Exposure During Pregnancy Form for Company-Sponsored Clinical Studies (458088-FOR) and should be provided for all pregnancies, regardless of the outcome.

Abnormal pregnancy outcomes (such as spontaneous abortion, foetal death, stillbirth, livebirth with congenital abnormalities (major and minor), ectopic pregnancy, termination of pregnancy, preterm birth, small for gestational age or foetal growth restriction, neonatal or infant death, and any other foetal or infant abnormalities that may be medically important) are considered SAEs.

Reports of pregnancy must be reported to Ipsen within 24 hours of the investigator's knowledge.

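### Pregnancy incidence is an endpoint for both cohorts, but the planned summary uses only the Safety Exposed Population, so it is not estimated for the unexposed cohort

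*Protocol*

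**What the plan says.** Section 8.2.2 has the objective "To describe the incidence of pregnancy" in its list for participants exposed and unexposed to palovarotene. Section 9.3.1.2 repeats it as an endpoint, "Incidence of pregnancy", under the heading "For participants with FOP exposed and unexposed to palovarotene". The pregnancy part of 9.7.3.4 then fixes the analysis: "Incidence of all pregnancies will be summarised for those exposed and unexposed to palovarotene in the Safety Exposed Population". The next sentence there defines an exposed pregnancy as one conceived while the participant is taking the drug or within 2 days of stopping, using the estimated conception date.

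Section 9.7.1 requires one or more doses of marketed palovarotene for the Safety Exposed Population, and no dose ever for the Safety Unexposed Population.

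Section 9.2.8 lists among the reasons for withdrawal from the registry: "For unexposed participants: the participant becomes pregnant or starts a treatment for FOP other than palovarotene". It adds: "Should the participant withdraw from the study, no further data will be collected". The same section has the date and primary reason of withdrawal entered in the eCRF and keeps the data gathered up to that point.

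**The concern.** The word *unexposed* has two meanings. In the objective and the endpoint list it names a cohort, the people never treated. In 9.7.3.4 it describes a pregnancy in someone who belongs to the treated population. A reader of 9.7.3.4 sees both words in one sentence and may assume that both cohorts are covered, when only one is.

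A stated secondary endpoint would then have no estimate for one of the two cohorts it names. A row headed unexposed in the final report could also be mistaken for the unexposed cohort.

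**Working it through.** No sample size, power or event-rate calculation applies. The check sets the sections side by side.

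1. **Scope of the endpoint.** 8.2.2 and 9.3.1.2 both place pregnancy incidence in the list that covers the two cohorts. The pregnancy outcome items (characteristics and outcomes, related adverse events, infant outcomes) stand in a separate list for exposed participants only. The protocol thus separates incidence (both cohorts) from outcomes (exposed only).

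2. **Population analysed.** 9.7.3.4 names the Safety Exposed Population and no other for incidence.

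3. **Overlap of the populations.** The Safety Exposed Population needs one dose or more; the Safety Unexposed Population needs none. They are disjoint, so the incidence table contains 0 members of the Safety Unexposed Population.

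4. **What the unexposed row can hold.** It can hold conceptions in treated participants more than 2 days after stopping and, conceivably, before the first dose in an incident user (Period 1 of 9.7.1). A member of the unexposed cohort who becomes pregnant is withdrawn under 9.2.8 before any first dose, so within that participation she does not move into the Safety Exposed Population.

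5. **Other places where it might be planned.** No other section plans pregnancy incidence in the Safety Unexposed Population. The nearest is Participant Disposition and Withdrawals in 9.7.3.5, which tabulates primary reasons for withdrawal. A pregnancy in the unexposed cohort could appear there as a count, without a denominator of time at risk.

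6. **Data available.**
   - Sex and date of birth are collected for all participants (9.3.2.1), where permitted and available.
   - Date and primary reason of withdrawal are recorded (9.2.8).
   - Table 4 and the unexposed visit lists (9.2.7.2 and 9.2.7.4) have no item for pregnancy or child-bearing status. Child-bearing status is assessed only for exposed participants (Tables 2 and 3, footnote h; 9.3.2.7).
   - A first pregnancy in the unexposed can thus be counted, but a denominator limited to those of child-bearing potential cannot be formed from the planned data.

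7. **Size.** The planned minimum is 67 exposed and 33 unexposed (9.7.2), so the omitted cohort is 33/(67 + 33) = 33% of the registry. Far fewer are at risk. The protocol sets no sex split. If enrolment reflects the absence of a sex predisposition noted in 7.1, about 33/2 ≈ 16 or 17 would be female, and about half of each cohort is to be paediatric.

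**The case against.** The strongest reply is that the protocol does not lose the information. Pregnancy is a named withdrawal reason in the unexposed cohort, the date and reason are recorded, and reasons are tabulated. That stands. A reader might infer from 9.2.8 that the endpoint is impossible to deliver for the unexposed, but withdrawal at pregnancy does not prevent counting a first pregnancy. The gap comes from the population named in 9.7.3.4. A disposition count is still not the incidence that 9.3.1.2 promises.

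A reader might also see a conflict between the withdrawal rule and 11.1.3.1, which says "Details of all pregnancies in participants will be collected from the signing of the ICF" and follows participants through the first postpartum year. The documents support this only weakly. Section 11 is headed for exposed participants, and outcome follow-up is an objective for exposed participants only. The sentence in 9.7.3.4 that promises outcome summaries irrespective of exposure can be read as exposure of the pregnancy. What remains is wording that should be made explicit.

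A third inference is that the 2-day conception rule contradicts the 30-day window for treatment-emergent events, or the testing rule in Table 2, footnote h ("pregnancy testing is carried out with a confirmation of absence of pregnancy monthly if the participant receives palovarotene and one month after stopping"). It does not. The three serve different purposes: classifying a conception, defining an adverse-event window and following the label on testing. Nothing says they must match.

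Nor does the protocol offer the unexposed row as a drug-free reference. The planned cohort comparison in 9.7.3.4 covers flare-ups, growth and bone fractures, not pregnancy.

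Finally, events will be few, and none was reported in the development programme (7.3.1). That limits what the missing estimate could show, but does not reconcile the sections.

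**Conclusion.** The inconsistency is real and narrow. Pregnancy incidence is promised for both cohorts and analysed in a population that by definition contains no never-treated participant. The endpoint is therefore not estimated for a cohort planned at 33 or more, of whom only the females of child-bearing age bear on it. The primary safety endpoints and the weighted comparison of key safety outcomes are untouched.

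The conclusion rests on reading *Safety Exposed Population* in 9.7.3.4 as 9.7.1 defines it. It does not rest on any assumed pregnancy rate or person-time: the protocol gives no basis for follow-up time in unexposed women of child-bearing potential, so no bound on the rate is offered. Choosing the analysis population is the protocol's own statement here, not a detail left open for the SAP, and it should be corrected at the source.

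**What to change.** Choose one of two routes.

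- **Keep the endpoint for both cohorts.** In 9.7.3.4, summarise pregnancy incidence in the Safety Exposed and the Safety Unexposed Populations. In the unexposed, count withdrawal because of pregnancy (9.2.8) as the event. Use follow-up time in female participants, by age group and ending at that withdrawal, as the denominator, because child-bearing status is not collected for them.
- **Narrow the endpoint.** Restrict the objective in 8.2.2 and the endpoint in 9.3.1.2, with the matching synopsis text, to exposed participants.

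Under either route, label *unexposed pregnancy* (conceived off drug within the Safety Exposed Population) separately from *unexposed cohort*. State also that the outcome summaries described as covering pregnancies irrespective of exposure refer to exposure of the pregnancy within the Safety Exposed Population, so that they agree with 9.2.8.

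Cost: the first route adds one population to a table and needs no new data item, since sex, date of birth, and withdrawal date and reason are already in the eCRF. Its downside is a row with very small counts and a denominator that includes females who are not at risk. The second route is wording only, and gives up the description for the unexposed cohort.
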